6. STUDY PROCEDURES

6.1 Pre-Study

Potential subjects will be referred by treating physicians for participation in this imaging study. The following procedures will occur pre-study:

- Review of eligibility criteria
- Obtain informed consent
- Collect demographics
- Review medical history, including any concomitant medication.

6.2 Imaging Days

Subjects will undergo one clinic visit for imaging. Subjects will receive an intravenous (IV) injection of investigational imaging agent (⁶⁸Ga-RM2) and undergo PET/MRI image collection as described above.

6.3 Follow-up

Active subject participation ends after the 24 to 72 hour post-scan Safety Follow-up. Investigators will follow subjects by chart review for 12 months post-scan (chart review of medical records at approximately 6 months post scan and 12 months post scan) to record any

standard of care biopsies or imaging results. The investigators will assist with identification of lesions that can be biopsied, based on ^{68}Ga -RM2 findings, if requested by treating physicians.

If a subject transfers clinical care outside of Stanford Healthcare during the chart review clinical follow-up period, investigators will request permission to contact the treating physician

6.4 Criteria for Removal from Study

The Protocol Director may withdraw subjects from the study for one or more of the following reasons: failure to follow the instructions of the Protocol Director and/or study staff; determination that continuing the participation could be harmful to the subject; the study is cancelled or other administrative reasons.

6.5 Alternatives

The alternative is to not participate in the study.

7. STUDY CALENDAR

	Pre-Study	Scan Date	24 to 72 Hours Post-Scan	12 Months
Informed consent	X			
Demographics	X			
Medical history	X			
^{68}Ga -RM2		X		
Safety Follow-up Call to Participant			X	
Data analysis				X

8. ADVERSE EVENTS AND REPORTING PROCEDURES

8.1 Potential Adverse Events

The administration of the radioactive substance will feel like a slight pinprick when given by i.v. injection. Patients who are claustrophobic may feel some anxiety while positioned in the scanner. Also, some patients find it uncomfortable to hold one position for more than a few minutes. The subjects will not feel anything related to the radioactivity of the substance in their body. Because the radioactivity is very short-lived, the radiation exposure is low. The substance amount is so small that it does not affect the normal processes of the body.

This research study involves exposure to radiation. This radiation exposure is for research purposes only. The amount of radiation from one ^{68}Ga -RM2 PET/MR is 4.76 mSv, approximately equal to 10% of the limit that radiation workers (for example, a hospital x-ray technician) are allowed to receive in 1 year. This amount of radiation involves minimal risk and is necessary to obtain the research information desired.

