2.3 Rationale

In this study, we propose to use a well-established PET isotope, Gallium-68 (^{68}Ga), bound to a bombesin receptor antagonist, ^{68}Ga -RM2, which has high affinity for gastrin-releasing peptide receptors. GRPR proteins are highly overexpressed in several human tumors, including breast cancer (2). The following aim is proposed:

To evaluate the feasibility of ^{68}Ga -RM2 PET/MRI for identification of ER+ primary breast cancer and metastases.

The first-in-human study investigated the safety, tolerability, metabolism, pharmacokinetics, biodistribution, and radiation dosimetry of ^{68}Ga -RM2. Five healthy men underwent dynamic whole-body PET/CT after an intravenous injection of ^{68}Ga -RM2 ($138 \pm 5 \text{ mBq}$). Besides total radioactivity, plasma samples were analyzed by radio-high-performance liquid chromatography for metabolism of the tracer. Dosimetry was calculated using the OLINDA/EXM software. The organs with the highest absorbed doses were the urinary bladder wall (0.62 mSv/MBq) and the pancreas (0.51 mSv/MBq). The mean effective dose was 0.051 mSv/MBq. ^{68}Ga -RM2 was well tolerated by all subjects. The authors concluded that the intravenously injected ^{68}Ga -RM2 is safe, and rapid metabolism is demonstrated. A 150-MBq injection of ^{68}Ga -RM2 results in an effective dose of 7.7 mSv, which could be reduced to 5.7 mSv with frequent bladder voids (5).

[figure not shown]

Figure 2: 74-year-old patient with a bilateral tumor with an ER/PR-positive tumor on the right side (PET-positive) and an ER/PR-negative tumor on the left side (PET-negative). Maximum intensity projection (left); CT (upper row); ^{68}Ga -RM2-PET (lower row); primary tumors indicated by red arrows (4).

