2.4 Study Design

This is a pilot study enrolling up to 20 participants with ER+ breast cancer, either at initial diagnosis prior to surgery or at suspected recurrence. Eligible participants will undergo baseline assessments at enrollment. Study participants will receive ^{68}Ga -RM2 and undergo a PET/MRI scan. All patients will first be seen by a Stanford Cancer Institute physician and then referred if appropriate on clinical grounds to [name] or his colleagues for this study. The following steps will take place.

1. Participants will be given a copy of the consent form s/he signed.
2. Participant will be asked to drink 1 to 2 glasses of water before arrival at the clinic
3. Vital signs (heart rate, blood pressure) will be recorded
4. Participant will be injected IV with $140 \pm 20\%$ mBq of ^{68}Ga -RM2
5. Participant will void immediately prior to the scan
6. Data acquisition will begin with a dedicated scan of the breasts, followed by a vertex to mid-thighs scan. First, localizer MRI scans will be performed to define the table positions and then MR structural imaging and diffusion weighted imaging will be performed simultaneously with PET imaging. After the dedicated scan of the breasts, a whole-body combined PET/MRI acquisition will be initiated with 3 to 5 table positions at a 2 to 4 minute acquisition time per table position.
7. Vital signs (heart rate, blood pressure) will be recorded again at the completion of the study, and the patient will be dismissed.
8. Participants will be contacted at 24 to 72 hours following the scan in order to collect record any adverse events.

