4. IMAGING AGENT INFORMATION

4.1 Study Agent ^{68}Ga -RM2

The PET radiopharmaceutical ^{68}Ga -RM2 has previously been identified as ^{68}Ga -DOTA Bombesin or BAY86-7548. This is not an FDA-approved product, and is described within IND 127137, the IND to which this protocol is submitted. The structure of ^{68}Ga -RM2 is represented in Figure 3.

BAY 86-7548

Figure 3: Chemical structure of ^{68}Ga -RM2

The administered dosage of ^{68}Ga -RM2 will be $140 \text{ mBq} \pm 20\%$, administered IV. The administered dosage is 140 mBq i.v. Measured human dosimetry data are available from published data (5). ^{68}Ga -RM2 is rapidly excreted through the kidneys to the urinary bladder and accumulated predominantly in the pancreas and liver. Maximum peak uptake of the total injected radioactivity was seen in the urinary bladder contents and the liver, with approximately 36% and 14%, respectively.

The organ with the highest absorbed dose was the urinary bladder wall at 0.61 mSv/MBq , followed by the pancreas at 0.51 mSv/MBq . The mean effective dose (14) was 0.051 mSv/MBq . Thus, the effective dose from a 140 MBq injected radioactivity is 7.7 mSv , which could be reduced to roughly 4.76 mSv with frequent bladder voiding (1-h voids).

To summarize the results of the published human dosimetry study, there were no observed adverse events to the radiopharmaceutical. The measured dosimetry showed that the critical organ with ^{68}Ga -RM2 is the urinary bladder, followed by the pancreas. The effective dose of ^{68}Ga -RM2 reported (0.051 mSv/MBq) is approximately twice as much as those of ^{68}Ga -DOTA-TOC (0.023 mSv/MBq), ^{68}Ga -DOTA-NOC (0.025 mSv/MBq), ^{68}Ga -DOTA-TATE (0.021 mSv/MBq) and ^{68}Ga -NOTA-RGD (0.022 mSv/MBq) (6-9).

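### Section 8.1 states 4.76 mSv per scan without condition, but section 4.1 gives that figure only for 1-hour voiding, which the listed procedure is not shown to meet

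*Combined protocol and SAP*

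**What the plan says.** Section 8.1 (Potential Adverse Events) tells the reader that the radiation from one "PET/MR is 4.76 mSv, approximately equal to 10% of the limit that radiation workers" may receive in a year. It adds that the exposure is for research only and describes the risk from this amount as minimal. Voiding is not mentioned.

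Section 4.1 gives an unreduced dose first: "Thus, the effective dose from a 140 MBq injected radioactivity is 7.7 mSv". It then gives the reduced value, "which could be reduced to roughly 4.76 mSv with frequent bladder voiding (1-h voids"). The same section reports a coefficient of 0.051 mSv/MBq and rests its comparison with other gallium-68 tracers on it: the effective dose "reported (0.051 mSv/MBq) is approximately twice as much as those of" four listed agents.

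Section 2.3 summarises the first-in-human study: "The mean effective dose was 0.051 mSv/MBq", and a 150 MBq injection "results in an effective dose of 7.7 mSv, which could be reduced to 5.7 mSv with frequent bladder voids".

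In the section 2.4 procedure, the tracer is injected at step 4. Step 5 reads "Participant will void immediately prior to the scan". The scan, a second set of vital signs and dismissal follow. No injection-to-scan interval is given, and no void after the scan is listed. Sections 5.2 and 6.2 and the study calendar add no voiding step.

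**The concern.** A value that section 4.1 makes conditional on a voiding schedule becomes unconditional in section 8.1, and the procedure that participants follow does not show that the schedule applies.

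Section 8.1 is where the protocol states the radiation risk of a scan done purely for research. Read alone, it gives only the lowest figure the documents print for 140 MBq, and it builds both the comparison with radiation workers and the minimal-risk description on that figure. A reader who checks it against sections 2.3 and 4.1 finds no single set of coefficient, activity and dose that agrees. If participant information took its number from section 8.1, the dropped condition would carry over. The consent form is not in the reviewed text, so that cannot be checked.

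**Working it through.** **Inputs.**
- Coefficient 0.051 mSv/MBq (sections 2.3 and 4.1).
- Nominal activity 140 with a tolerance of 20% either way (sections 2.4 and 4.1), taken in MBq as in section 4.1's dosimetry sentence. The tolerance gives 112 to 168 MBq.
- Stated doses: 4.76 mSv (sections 4.1 and 8.1); 7.7 mSv at 140 MBq (section 4.1); 7.7 mSv, reducible to 5.7 mSv, at 150 MBq (section 2.3).

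**Formula.** Effective dose (mSv) = coefficient (mSv/MBq) × activity (MBq).

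**1. Reproducing the plan's figures.**
- Section 2.3: 0.051 × 150 = 7.65, which rounds to the printed 7.7. It agrees.
- Section 4.1, unreduced: 0.051 × 140 = 7.14, not 7.7. The difference is 0.56 mSv, and 7.7/7.14 = 1.078, about 8% high against the section's own coefficient. Back-solved, 7.7/0.051 = 151 MBq, so the figure fits section 2.3's activity.
- Section 8.1: 4.76/140 = 0.034 mSv/MBq, a coefficient the documents do not print. At 0.051, a dose of 4.76 mSv would need 4.76/0.051 = 93.3 MBq, below the 112 MBq lower tolerance. The activity range therefore does not explain it; only the reduction for voiding does.

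**2. The two reduced figures.** Section 2.3: 5.7/150 = 0.038 mSv/MBq. Section 4.1: 4.76/140 = 0.034 mSv/MBq. Section 2.3's value carried to 140 MBq is 0.038 × 140 = 5.32 mSv, against 4.76. Section 4.1 names a 1-hour interval and section 2.3 names none, so different intervals could account for this.

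**3. Is the 1-hour condition met?** Section 2.4 lists one void at an unspecified time after injection. The earlier prostate pilot (section 2.1) imaged at 42 to 51 minutes, so a first void within the hour is plausible. This protocol sets no such interval and lists nothing after the scan.

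**4. Size at nominal activity.** 4.76 mSv with 1-hour voids; 7.14 mSv at the stated coefficient; 4.76/7.14 = 67%. The worker limit is not stated, so I scale section 8.1's own 10%: 10% × 7.14/4.76 = 15%. If the approximate 10% is assumed to mean 9.5% to 10.5%, the result is 14.3% to 15.8%. With section 4.1's printed 7.7 mSv it is 10% × 7.7/4.76 = 16.2%.

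**5. Over the activity tolerance.**

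| Activity (MBq) | At 0.034 mSv/MBq | At 0.051 mSv/MBq | Share of worker limit, scaled |
|---|---|---|---|
| 112 | 3.81 mSv | 5.71 mSv | 8% to 12% |
| 140 | 4.76 mSv | 7.14 mSv | 10% to 15% |
| 168 | 5.71 mSv | 8.57 mSv | 12% to 18% |

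**6. Basis of the tracer comparison.** The listed tracers run from 0.021 to 0.025 mSv/MBq. With 0.051 the ratio is 2.0 to 2.4, as section 4.1 says. With the 0.034 implied by section 8.1 it would be 1.4 to 1.6. The comparison and the risk statement use different bases.

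**The case against.** The strongest reply is that no wrong dose has been shown. Section 8.1 repeats section 4.1's 4.76 mSv exactly. The listed void comes after injection and may well fall within an hour. The voiding interval behind 0.051 is not given, so 7.14 mSv is not established as the dose participants receive. All of this stands. What is shown is a dropped condition and a set of figures that do not agree, not a measured excess.

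It is also fair that sections 2.3 and 4.1 print the higher doses and the 1-hour condition, so a reader of the whole protocol can find them. That limits the harm but does not correct section 8.1, whose percentage and risk description rest on 4.76 mSv alone.

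Several items carry little weight by themselves. The 7.7 mSv slip is about 8% and overstates the dose. The activity tolerance affects any dose quoted at nominal activity. The tracer comparison in section 4.1 is correct for the coefficient it uses. The two reduced figures may reflect different voiding intervals. The mBq and MBq printings are a matter of letter case, and the intended unit is clear from section 4.1. They belong in the same correction, but the concern does not depend on them.

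**Conclusion.** The concern holds. Section 8.1 states as the exposure from one scan a figure that section 4.1 offers only under 1-hour voiding, and the listed procedure does not show that this condition is met. At 140 MBq the documents support a range from 4.76 mSv (1-hour voids) to 7.14 mSv (stated coefficient), or about 10% to 15% of the worker limit on section 8.1's own scale. That gap is the distance to the unreduced figure. Section 8.1 may understate exposure, but by how much, if at all, cannot be settled from these documents.

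The result assumes activity in MBq and takes section 8.1's 10% as the scale, since the limit itself is not given. I make no claim that a higher figure would change the minimal-risk description. The correction should be made because this is the protocol's own statement of research radiation risk. Design, sample size and analysis are unaffected.

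**What to change.** - **Section 8.1:** attach the 1-hour voiding condition to 4.76 mSv, print the unreduced figure beside it once sections 2.3 and 4.1 agree, and give the worker-limit percentage for both.
- **Sections 2.3 and 4.1:** make coefficient, activity and effective dose agree. In particular, 7.7 mSv cannot follow from 0.051 mSv/MBq at both 140 and 150 MBq. State the voiding interval behind each reduced figure (0.038 and 0.034 mSv/MBq) and behind 0.051.
- **Section 2.4 against sections 4.1 and 8.1:** reconcile the listed voiding step with the condition on which the stated dose depends.
- **Units:** use one form of the activity unit. Section 4.1 reads "The administered dosage is 140 mBq i.v" and then uses MBq in its dosimetry; sections 2.3 and 2.4 also print mBq.

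No change to the administered activity or to the voiding procedure is proposed. The cost is wording and figure corrections in four sections; the one drawback is that the exposure stated in section 8.1 will look less favourable.

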8.2 Adverse Event Reporting

We do not anticipate hazardous situations for the subjects as a result of this protocol. However, standard of care procedures will be in place for verification of correct radiopharmaceutical dose and route of administration. The study Principal Investigator (PI) or his designee will report all serious adverse events (per 21CFR§312.32) to the Stanford CCTO Safety Coordinator within 10 working days of becoming aware of the event (5 days if the event is life-threatening or resulted

in death) using the Adverse Events Communication Form. If the principal investigator determines the unanticipated adverse device effect presents an unreasonable risk to subjects, the study will be terminated as soon as possible, but no later than 5 working days after the PI makes the determination and no later than 15 working days after first receiving notification of the effect.

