9.2 Data Management Plan

The study charts will be stored in a locked office in the Cancer Clinical Trials Office. Demographic information will be kept using OnCore.

During the clinical investigation, the Protocol Director will evaluate the progress of the trial, including periodic assessments of data quality and timeliness, participant recruitment, accrual and retention, participant risk versus benefit, performance of trial sites, and other factors that can affect study outcome.

The Stanford Cancer Institute Data and Safety Monitoring Committee (DSMC) will audit study related activities to determine whether the study has been conducted in accordance with the protocol, local standard operating procedures, FDA regulations, and Good Clinical Practice (GCP). This may include review of regulatory binders, case report forms, eligibility checklists, and source documents. In addition, the DSMC will regularly review serious adverse events and protocol deviations associated with the research to ensure the protection of human subjects. Results of DSMC audits will be communicated to the IRB and the appropriate regulatory authorities at the time of continuing review, or in an expedited fashion, as needed.

10. Statistical Considerations and Evaluation of Results

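### The only study-level termination rule with deadlines (section 8.2) is triggered by a device effect, although the investigational product is an injected drug tracer under an IND: wrong as written, minor in weight

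*Combined protocol and SAP*

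**What the plan says.** Section 8.2 (Adverse Event Reporting) does two things. First, it sets a reporting duty: the PI or a designee "will report all serious adverse events (per 21CFR§312.32") to the institution's safety coordinator "within 10 working days of becoming aware of the event", shortened to 5 days for life-threatening or fatal events.

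Second, it sets a termination duty. If the PI determines that "the unanticipated adverse device effect presents an unreasonable risk to subjects", the study must be terminated as soon as possible. One outer limit is "no later than 5 working days after the PI makes the determination". The other outer limit, which has its own starting point, is "no later than 15 working days after first receiving notification of the effect".

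On the product, section 4.1 calls 68Ga-RM2 a PET radiopharmaceutical and states: "This is not an FDA-approved product, and is described within IND 127137". The synopsis lists it as the sole investigational product, and section 6.2 gives the route as intravenous injection.

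On oversight, section 9.2 says that "the DSMC will regularly review serious adverse events and protocol deviations associated with the research". The results of its audits go to the IRB and regulatory authorities "at the time of continuing review, or in an expedited fashion, as needed".

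**The concern.** The termination sentence names the wrong kind of product. A PI or auditor who applies it word for word would find that a serious reaction to the injected tracer is not a device effect. The obligation to terminate, and the two limits attached to it, would then not apply to harm from the one agent under investigation.

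This is operative text that protects participants, not background. Section 9.2 has conduct audited against the protocol, so the wording also decides what an audit can hold the study to. What is at stake is the mandatory character and timing of termination. The estimate of sensitivity and its interpretation are not involved.

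**Working it through.** No formula applies. The check sets the relevant sections side by side.

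1. **Is there an investigational device?** The synopsis lists only 68Ga-RM2. Sections 2.1 and 4.1 place it under IND 127137, and section 6.2 has it injected intravenously. Section 5.1 names PET/MRI, but only as the imaging modality. The word *device* occurs once in the available text, in the termination sentence itself.

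2. **Does the phrase refer back to anything?** It carries a definite article, but no device effect has been mentioned or defined before it. The sentence immediately before concerns serious adverse events and cites 21 CFR 312.32. Section 4.1 puts the product under an IND, so the reporting half of 8.2 is written for a drug and the termination half for a device.

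3. **Could the scanner be the device?** That reading gives the phrase a meaning, but it still leaves the tracer outside the rule.

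4. **Does another section fill the gap?**
   - Section 6.4 lets the Protocol Director withdraw an individual participant for harm. It lists cancellation of the study as a reason for withdrawal, but gives no criterion for cancelling and no deadline.
   - Section 9.2 has the Protocol Director weigh risk against benefit periodically and the DSMC review serious events. It states no stopping criterion and no deadline.
   - The reporting limits in 8.2 (10 working days, or 5 days) govern notification, not termination.

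5. **Could the text be damaged?** The sentence is complete and legible, with no redaction. It is current protocol text, not an amendment summary.

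Result: in the available text, 8.2 holds the only study-level termination rule with deadlines, and its literal trigger excludes a reaction to 68Ga-RM2. The opening pages and the text between sections 4.1 and 4.3 were not available, so the word *only* is limited to what could be read.

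**The case against.** The strongest reply is that nobody would read the sentence literally. It follows directly on serious adverse event reporting, and with no other antecedent its definite article most naturally points back to such an event. The phrase looks like wording carried over from elsewhere, although the documents do not show its origin. This reply largely stands, and it is why the point is minor. It does not make the sentence correct.

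A second reply is that little is lost in practice. The PI must judge the risk unreasonable under either wording, and nothing prevents a PI who reaches that view from stopping. Each participant has a single imaging visit with one injection. This also stands. What the literal wording removes is the duty to terminate and its time limits, not the power to stop.

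A third reply is that the tracer has been well tolerated. The text reports this for 5 healthy men (section 2.3) and 10 men with prostate cancer (section 2.1). With no events in 5 + 10 = 15 people, and treating them as comparable, the one-sided 95% upper limit for the event rate is 1 − 0.05^(1/15) ≈ 18%. Section 2.1 also mentions 81 and 16 prostate cancer patients in ongoing studies, but gives no safety results for them. This record is reassuring, but a termination rule exists for the unlikely event.

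A reader might also infer that the rule should be widened to anticipated events that prove too frequent or too severe. The documents show no defect in limiting the rule to unanticipated events. Widening it would change its scope, not correct its wording.

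**Conclusion.** The termination trigger in 8.2 is wrong as written and should be corrected. The weight is minor: the intent is probably clear, the PI can stop the study regardless, and reporting and DSMC review of serious events continue. There is no effect on the sample size, the endpoint or the analysis.

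Three stronger readings are not supported:

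- **That the study cannot be stopped for a tracer reaction.** Section 6.4 foresees cancellation, and section 9.2 provides for review of risk and of serious events.
- **That the wording exposes more participants to harm.** The documents give no basis for deriving an excess, and none is claimed.
- **That the study lacks any binding limit or breaches a regulation.** The FDA regulations and local procedures mentioned in section 9.2 may set their own limits, which cannot be checked from these documents.

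The conclusion rests on the literal wording of 8.2 and on the pages not available containing no separate termination rule.

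**What to change.** In the termination sentence of section 8.2:

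- Replace the device-effect trigger with *an unanticipated adverse event associated with 68Ga-RM2 or the study procedures*. The PI's determination of unreasonable risk remains the controlling condition.
- In the second time limit, refer to notification of the *event* instead of the effect.
- Keep both limits, 5 and 15 working days, as they are.

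This keeps the restriction to unanticipated events, brings the tracer under the rule, and covers harm from the scan through the reference to study procedures.

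The cost is a one-sentence modification, approved by the IRB before implementation as section 9.1 requires. Enrolment, data collection and analysis do not change.
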